## **12.0 CRITERIA FOR EVALUATION AND ENDPOINT DEFINITIONS**

- **Distress screening:**
  - PHQ instrument was completed by the patient either during an oncology-related visit or online within 10 days pre- or post-visit.
  - Score of PHQ (continuous) and categorized to low, medium, high score
- **Utilization:**
  - Number of urgent care visits and associated diagnostic codes
  - Number of emergency department visits and associated diagnostic codes; subsequent discharge or hospitalization
  - Hospitalizations, length of stay, and associated diagnostic codes
  - Primary care visits
  - Medical oncology visits
  - Behavioral health visits
  - Number of referrals to behavioral health services
- **Patient-reported outcomes:**
  - Fact-B Functional Well-Being (Likert scale, 0-28)
  - Fact-B Social/Family Well-Being (Likert scale, 0-28)
  - Fact-B Emotional Well-Being (Likert scale, 0-24)
  - Fact-B Functional Well-Being (Likert scale, 0-28)
  - Breast Cancer Subscale (Likert scale, 0-40)

## **13.0 DATA COLLECTION AND MONITORING**

- 13.1 **Screening.** Newly diagnosed breast cancer patients will be offered the PHQ screening tool at the initial consult visit within oncology as part of usual care. Patients will have the right to refuse completing the tool. The PHQ is already built into the electronic medical record with results available in a dedicated PHQ results tables in Clarity (the backend of electronic medical record). Questionnaire data will be entered into the medical record by the screening LVN, MA or RN and we will capture data from the PHQ database. Patients may also be offered screening at subsequent visits.
- 13.2 **Referrals.** We will access referral data using Tapestry, a database linked to the KPSC electronic medical record that records all referral activities, including those to behavioral health services.
- 13.3 **Utilization of health care services:** To compare patient utilization of health services between intervention and control sites, we will capture utilization of health services from our electronic medical record using Current Procedural Terminology (CPT) and International Classification of Disease (ICD) codes as appropriate.
- 13.4 **Covariate and breast cancer treatment data.** We will collect covariate information from the electronic health record and data from the KPSC tumor registry.
- 13.5 **Surveys.** We will invite all newly diagnosed breast cancer patients at the intervention and control sites to complete two short patient-reported outcome surveys, the Functional Assessment of Cancer Therapy for Breast Cancer (FACT-B) and the Breast Cancer Prevention Trial Symptom Checklist (BCPT). Those who agree to participate will be asked to complete these two brief surveys at 3 time points (3-, 6- and 12-months).
- 13.6 **Standardized data collection.** Data collection from the electronic record for screening, referral, and utilization data will use standardized approaches to ensure equitable collection of high-quality data.

- 13.7 **Security.** All data files will be kept on a secured shared drive with access restricted to project staff using password-protected computers. Initially, research and medical records will be used to build the analytic databases. Each subject will be assigned a unique study identification number and all other identifiers will be removed as early as possible without compromising the conduct of the study. The linkage file between study identification number and medical record number will be stored separately on a password-protected server accessible only to the principal investigator, project manager, research associates, and programmer/analysts. Confidentiality of patient information will be protected by using password-protected computers for all data analysis and management, as well as keeping confidential information printed on hard copies in locked file cabinets within the Department of Research & Evaluation. Only project staff will have access to confidential information; staff have been trained in compliance and working with protected health information.
- 13.8 **Quality monitoring.** Weekly quality monitoring checks with the study team to monitor screening and referrals will occur. Study information will only be shared among project staff as needed to complete the study objectives using standard Research & Evaluation practices, including password-protected files on restricted-access secured shared drives. Emails will be encrypted if data will be sent between project staff; however, emails will be minimized as weekly quality monitoring checks with the study team to monitor screening and referrals will be conducted in-person whenever possible.
- 13.9 **Recruitment.** Recruitment oversight for participant surveys will be conducted by the study team, with data checks via team meetings and RedCap reporting statistics. Emails will be encrypted if data will be sent between project staff; however, emails will be minimized as weekly in-person study team meetings will occur whenever possible to conduct data checks and review updated reporting.

#### **14.0 STATISTICAL CONSIDERATIONS**

**Aim 1: Evaluate the effectiveness of a guideline-recommended distress screening program for breast cancer patients in improving identification of distressed patients, initiation and completion of referrals to behavioral health, and patient-reported and utilization outcomes as compared to usual care within KPSC, using a pragmatic cluster randomized control trial design.**

- 14.1 **Power and sample size.** Of the 14 KPSC medical centers, we have selected 6 centers with the highest average number of new breast cancer cases diagnosed between 2011 and 2014. Based on the average number of cases. We expect a total of at least 1,200 newly diagnosed patients across the 6 sites, and to enroll anywhere from 50 to 300 newly diagnosed breast cancer patients per intervention site, entering all such cases into our cohort with no exclusions. We performed cluster randomization to select the intervention and control sites. While cluster randomization may be less statistically efficient than individual randomization, we believe it makes the study more feasible for several reasons. First, it allows us to truly evaluate the effectiveness of the distress screening program, with the screening offered to all newly diagnosed patients in the intervention centers. This will provide real-world information on uptake and effectiveness. Second, it allows us to avoid contamination between the distress screening intervention and other possible competing interventions, as well as outside information that may be publicly available to patients. Third, it allows us to balance (on average) medical center-level factors that we are otherwise unable to measure reliably. For all outcomes, we expect relatively small standardized effect sizes (measured in terms of z-scores) ranging from 0.2-0.4, because this is an effectiveness study. To achieve 80% power with a significance level of 0.05, our per-center sample size requirement ranges from as few as 20 for large effect size (0.4) and zero intraclass correlation (ICC), to about 400 for small effect size

and large ICC (0.2 and 0.01, respectively). Given that we can expect 50 to 300 newly diagnosed breast cancer patients per center, we should be adequately powered to detect effect sizes as small as 0.2, given ICCs no greater than 0.007. This is a lower bound on our power, since we expect to have as many as 200 more patients at some medical centers, and so our power is most likely greater than reported here.

- 14.2 Statistical analysis plan: All variables will be described with summary statistics appropriate for measurement type, such as frequency and percent, mean, median, standard deviation, minimum, and maximum. Patterns of missing values will be examined and evaluated for randomness using the method described by Enders. Diagnostic plots and inferential tests for tenability of assumptions will be evaluated for our primary and secondary outcomes, and appropriate remedial methods (e.g., Box-Cox transformations) applied where required. We will analyze referral and utilization outcomes as the total amount of services used during the study period, and use said diagnostic tests to determine the best modeling strategy for examining relationships with relevant demographic and clinical characteristics, exploring potential disparities by race/ethnicity and socioeconomic status. If necessary, we will analyze relationships with referral and utilization outcomes using Poisson or Negative Binomial regression models. We will use an intent-to-treat analysis, including data on all newly diagnosed patients in the intervention and control groups without regard to their screening status, appropriate for a cluster RCT.

Patient-reported outcomes from our mailed patient surveys (FACT B and BCPT) will be subjected to the same diagnostic testing as the utilization outcomes. To account for having repeated measurements for these patient-reported outcomes (3, 6, and 12 months post-diagnosis), we will use generalized estimating equations or linear mixed effects models, for situations where no or some repeated measures are missing, respectively. We will also analyze patient-reported outcomes using non-parametric regression techniques, such as quantile regression, to assess the sensitivity of our findings to other key modeling assumptions. Additionally, to analyze any improvement in identification of highly distressed patients by the systematic screening program, we will compare patients reporting high levels of distress on the FACT-B with patients receiving referral for high-level distress services (psychiatry, psychology). Statistical analyses will be conducted using SAS, R and/or MPlus. The study team will meet regularly to review adherence to the study protocol, evaluate study progress, and identify and resolve issues. Frequencies tables will be examined and out-of-range checks of all variables will be conducted, and results checked for consistency. Our advocate and advisors will provide insights and suggestions to guide our analyses to ensure we are considering a broad range of views

**Aim 2: Identify patient-, clinician-, and system-level barriers and facilitators to implementation of the program, and assess stakeholder-perceived acceptability, fidelity, and achievements of the program**

- 14.3 Study Population and Identification. Using semi-structured interviews with key stakeholders, including medical oncologists, breast cancer care coordinators and/or navigators, licensed clinical social workers, oncology nurses (RNs, LVNs or MAs), oncology operational leaders, and breast cancer patients, we will identify barriers and facilitators to program implementation of large-scale distress screening. Our target sample size is 30. We will identify key informants in collaboration with [name], our oncology advisor who is a senior leader in KPSC oncology clinical practice as well as an operational leader within KPSC as Assistant Medical Director of the Southern California Permanente Medical Group. We will also use snowball sampling, a purposeful non-probability sampling technique, asking participants to identify other key informants that we may have overlooked. Potential patient participants will be identified in collaboration with our clinical participants, as well as with the KPSC Regional Medical

Advisory Council (RMAC), a member-led council that provides feedback to KPSC clinicians, researchers, and operational leaders on a variety of topics. RMAC has sub-councils for disease specific groups, including oncology. We will target breast cancer patients 1 to 3 years post-diagnosis to gain insights into how distress screening could be integrated most effectively throughout the cancer care continuum.

- 14.4 Qualitative data management. One-to-one interviews will be conducted in person or over the telephone by the research study team. We estimate that each interview will take between 35 and 45 minutes to complete. We will obtain oral consent from each participant prior to the beginning of each interview. All interviews will be recorded and transcribed. Our analysis will focus on thematic development related to barriers and facilitators to implementation, guided by the domains from the Consolidated Framework for Implementation Research. We will develop a coding structure inductively, using the constant comparative method, and with input from our advocate, co-investigators, and oncology consultant. Codes may include concept and sub-concept codes, relationship codes, and participant perspective and characteristic codes. Consensus on the coding structure will be achieved via iterative testing of structure development by members of the research team, followed by review and resolution of discrepancies and discussion with our advocate and advisors. To help ensure rigor and transparency, all coding development steps will be tracked and reported. All analyses will be performed using appropriate qualitative analytic software (ATLAS.ti, version 7.5.10).
- 14.5 Qualitative interviews. We will use CFIR to identify relevant domains, including: 1) *Acceptability*, or the perception that the program is satisfactory; 2) *Fidelity*, or the degree to which the program was implemented as prescribed, typically measured by comparing the planned intervention and the actual intervention in terms of adherence to the protocol; and 3) *Adoption*, or “uptake” of the program. We will use Helfrich et al.’s (2009) Organizational Readiness to Change Assessment, a validated survey instrument which operationalizes the CFIR domains for measurement and has been mapped to each construct, to develop questions regarding contextual factors. This information will be critical in aligning the program with provider and system-level needs to facilitate dissemination, scale-up, and spread throughout KPSC, to KP nationally, and other health care settings.

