- 4.4 **Method of screening:** We are using PHQ, a recommended distress screening instrument (the PHQ is available in multiple languages). This instrument has been shown to be a valid, reliable tool with high sensitivity and specificity for measuring distress in the cancer population. The instrument is also credible and acceptable to KPSC clinicians and the PHQ are already built into the KPSC electronic health record. The screening will be offered as part of usual care at the intervention sites. Patients are free to refuse distress screening.
- 4.5 **Adaptive workflow design and responsibility of screening program:** We have developed an adaptive approach to the screening workflow, where the screening process can be completed differently at intervention sites depending on local context and resources. While the timing of the screening (e.g., initial visit, follow-up visit), instrument, scoring, and referral algorithm remains the same across all intervention sites, the type of staff overseeing the screening, screening mode (e.g., on paper, entered into computer), and place of screening during the visit (e.g., while in waiting room, while in exam room) can vary. As recommended in the guidelines, we have identified specific staff embedded in the oncology breast care teams to be the main points of contact for the screening program. These staff include: Oncology Department Administrators (DAs) and Assistant Department Administrators (ADAs), as well as oncology RNs, LVNs, MAs, and social workers where appropriate. Accountability and oversight of screening at each site can

vary per local context. We have provided ongoing training and support to the clinical care teams identified at each intervention site (implementation facilitation).

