- 4.8 **Identification of participants for patient-reported outcome surveys.** All eligible patients who speak English or Spanish will be invited to participate in a survey of patient-reported outcomes. We will confirm if the potential participant has an active email address via our membership databases. Those who do will be initially contacted via email; those who do not will be initially contacted via postal mail (see contact workflow descriptions, below). Those who agree to participate will be asked to complete these two brief surveys at 3 time points (3-, 6- and 12-months). We will alert the oncology teams at all participating medical centers, as well as KPSC Member Services, in advance so that they are aware of the survey administration schedule and prepared to address any patient questions about the surveys and/or the study.
- 4.9 **Survey administration and tracking:** We will use RedCap software for all recruitment and survey tracking, as well as for on-line consenting and administration of the surveys whenever possible (e.g., for all patients with a viable email address), as well as for tracking postal mail and phone recruitment contact attempts.
- 4.10 **Outcomes:**

Primary. Our primary outcome is percent of eligible patients screened and referred (based on PHQ score) at intervention versus control sites.

Secondary. Our secondary outcomes include: completion of recommended referrals, utilization of outpatient medical oncology visits, primary care visits, behavioral health visits, urgent care visits, and emergency department visits; we will also examine patient-reported outcomes using the Functional Assessment of Cancer Therapy-Breast survey, and the Breast Cancer Prevention Trial (BCPT) Symptom Checklist.

***Please note: We received a waiver of written informed consent for the electronic health record data collection aspect of the study to identify newly diagnosed breast cancer patients at intervention and control sites during the screening intervention period (12 months) on September 22, 2016; we received a waiver of written informed consent for the survey portion of the study on May 8, 2017.***

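### Section 14.1 claims adequate power for all outcomes, including the primary percent, without stating arm percents or an ICC for it, and three centres per arm do not deliver that claim

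*Combined protocol and SAP*

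**What the plan says.** Section 4.10 defines the primary outcome as a percent: "Our primary outcome is percent of eligible patients screened and referred (based on PHQ score) at intervention versus control sites". Section 3.0 sets three intervention and three control centres, with 600 patients expected in each arm.

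Section 14.1 is the only power statement. It covers the primary outcome by its opening words: "For all outcomes, we expect relatively small standardized effect sizes (measured in terms of z-scores) ranging from 0.2-0.4, because this is an effectiveness study". On sample size it says "To achieve 80% power with a significance level of 0.05, our per-center sample size requirement ranges from as few as 20" (0.4 SD, ICC zero) "to about 400 for small effect size" "and large ICC (0.2 and 0.01, respectively"). From 50 to 300 patients per centre it concludes that power is adequate down to 0.2 SD, "given ICCs no greater than 0.007". It then calls this a lower bound, because some centres may supply more patients.

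The section gives no expected percent for either arm, no difference in percentage points, no ICC for the primary outcome, no source for its ICCs and no sidedness.

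Section 4.5 lets three things differ between intervention sites: "the type of staff overseeing the screening, screening mode (e.g., on paper, entered into computer), and place of screening during the visit". The same sentence holds timing, instrument, scoring and referral algorithm fixed.

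**The concern.** The claim of adequate power extends to the outcome on which the trial will be judged, but a reader cannot tell what difference in percent it refers to or what between-centre variation it allows for. With six centres, power for a percent that the sites themselves deliver depends heavily on how far centres differ, and much less on the number of patients. If power is lower than the plan asserts, a real gain in screening and referral could come out non-significant and be read as failure of the program.

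**Working it through.** **Inputs.** From the plan: k = 3 centres per arm and 600 patients per arm, so m = 200 per centre on average (3.0); 5% significance, 80% power, 0.2 to 0.4 SD, ICC 0 to 0.01 (14.1). Assumed: two-sided test, equal centre sizes, the same ICC in both arms, control rates of 5% and 10%, and ICCs above 0.01.

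**Step 1: the plan's own figures.** SE = sqrt(2[1 + (m − 1)ICC]/(km)), with power from a noncentral t on 2(k − 1) df; the normal approximation follows in brackets. For k = 3:

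- 0.4 SD, ICC 0, m = 20: SE = sqrt(2/60) = 0.183, ratio 2.19, power 39% (59%). Reaching 80% needs 59 per centre (33), not 20.
- 0.2 SD, ICC 0.01, m = 400: SE = sqrt(2 × 4.99/1200) = 0.0912, ratio 2.19, power 39% (59%). With unlimited patients, SE = sqrt(2 × 0.01/3) = 0.0816 and power stops at 46% (69%).
- 0.2 SD, ICC 0.007, m = 200: SE = sqrt(2 × 2.393/600) = 0.0893, ratio 2.24, power 40% (61%).

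None of the stated figures is reproduced. All three are with k = 6 per arm and 10 df: 21 per centre (stated 20), 412 (stated about 400), and a largest ICC of 0.0074 at 200 per centre (stated 0.007).

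**Step 2: the same claim in percent.** Cohen's h = 2·arcsin√p₁ − 2·arcsin√p₀. Setting h = 0.2 and p₀ = 10% gives p₁ = 16.8%, about 17%. The variance of a centre's percent is p(1 − p)[ICC + (1 − ICC)/200]. At ICC 0.007 the bracket is 0.007 + 0.993/200 = 0.01197. Then SE = sqrt((0.0900 + 0.1411) × 0.01197/3) = 0.0304, ratio 0.07/0.0304 = 2.31, and power is 42% on 4 df (64% by normal approximation).

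**Step 3: smallest intervention percent with 80% power** (same variance, 4 df):

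| ICC | from 10% | from 5% |
|---|---|---|
| 0.007 | 22% | 15% |
| 0.01 | 24% | 16% |
| 0.05 | 39% | 31% |
| 0.10 | 51% | 43% |
| 0.20 | 65% | 58% |

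**Step 4: power for two larger contrasts.** For p = 40% and p = 60% alike, p(1 − p) = 0.24, so the SE is the same. At ICC 0.10 it is sqrt(0.33 × 0.1045/3) = 0.107; the ratios are 0.30/0.107 = 2.80 and 0.50/0.107 = 4.66.

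| ICC | 10% v 40% | 10% v 60% |
|---|---|---|
| 0.05 | 82% | >99% |
| 0.10 | 56% | 93% |
| 0.20 | 34% | 71% |

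**Step 5: what an ICC means here.** Between-centre SD = sqrt(ICC × p(1 − p)). At 60% and ICC 0.01 this is sqrt(0.0024) = 4.9 points. Centres at 50, 60 and 70% give 0.01/0.24 = 0.04; centres at 40, 60 and 80% give 0.04/0.24 = 0.17.

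**Step 6: the lower-bound sentence.** Effective size per centre is m/[1 + (m − 1)ICC]. At ICC 0.10, 200/20.9 = 9.6 and 400/40.9 = 9.8. Doubling a centre adds almost nothing.

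**The case against.** A reader might infer that the trial is underpowered for its primary outcome. The documents do not support that. The control rates, the 40% and 60% targets, the ICCs above 0.01 and the 4-df test are all assumptions. An ICC of 0.20 at a control mean of 10% implies a between-centre SD of sqrt(0.20 × 0.09) = 13 points, larger than the mean itself. If control centres vary little (ICC 0.01), 10% v 40% at an intervention ICC of 0.10 has 67% power instead of 56%. The spreads in Step 5, tested as 10% v 60%, give over 99% (ICC 0.04) and 77% (ICC 0.17). For 10% v 70%, power is 87% even at ICC 0.20.

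A reader might also infer that 0.2 to 0.4 SD is the wrong effect for this program. That does not follow either. A small assumed effect is conservative. Whether it is too small depends on which referrals count: 4.6 sends low scorers to Health Education and 5.2 counts that service, while Aim 1 speaks of behavioral health and the pathways listed in 4.7 omit health education.

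Nor is large variation between sites established. Section 4.5 fixes timing, instrument, scoring and referral algorithm, and audit, facilitation (4.1) and weekly monitoring (13.8) should narrow differences.

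These objections limit what can be said about the true power. They leave the stated claim unsupported: at 0.2 SD and ICC 0.007, the plan's own values, power with three centres per arm is well below 80% by t or by normal approximation.

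**Conclusion.** The concern holds in this form: 14.1 asserts adequate power for the primary percent without stating it in that outcome's terms, and the assertion fails for three centres per arm. At the plan's own limit (0.2 SD, ICC 0.007) power is about 40% in SD units, or 42% as 10% v 17%, with 200 per centre and 4 df.

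From a 10% control rate, the smallest percent detectable with 80% power runs from about 22% at ICC 0.007 to about 65% at ICC 0.20. ICCs above 0.01 are plausible, because sites deliver the outcome and parts of the workflow may vary, but they are not certain. Real power could therefore be ample or poor, and the plan does not let a reader tell which. Unequal centres within the stated 50 to 300 would lower it further.

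That six centres per arm were entered in place of six in total is an inference from the match in Step 1; the documents do not say so.

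**What to change.** In 14.1:

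- Replace the adequate-power conclusion for the primary outcome with a statement in percentage points for three centres per arm and 4 df. Give the minimum detectable intervention percent for control rates of 5 to 10% and ICCs of 0.007 to 0.20, and state the sidedness.
- Delete the lower-bound sentence for this outcome.
- Do not retain the existing 0.2 to 0.4 SD and ICC 0.01 figures for the secondary outcomes. Recompute them for three centres per arm.

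The cost is a rewritten paragraph and a small table. The stated power becomes less favourable. The centres are already randomized, so this changes what is disclosed and not the power itself; no extra patients or sites are needed.

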## **3.0 STUDY DESIGN**

We will use an effectiveness-implementation hybrid study design that allows for simultaneous study of the clinical effectiveness and implementation of distress screening to address the need for evidence in both areas. Hybrid designs have *a priori* focus on assessing outcomes relevant to both effectiveness of an intervention and implementation-related outcomes. We will employ a sequential mixed methods study design that integrates qualitative and quantitative methods, as is appropriate to address the proposed research questions. Our highly pragmatic approach is guided by the Pragmatic-Explanatory Continuum Indicator Summary-2 with adaptive workflow design. We will use the Consolidated Framework for Implementation Research (CFIR) to guide collection and analysis of implementation outcomes.

[figure not shown]
We will use cluster randomization at the medical center level. There will be 6 KPSC medical centers participating in total: 3 intervention sites and 3 control sites.

The screening program will be implemented at the 3 intervention sites, offering the program to all newly diagnosed breast cancer patients within the intervention site over a 12-month period with no exclusions. Under the intervention condition, distress screening using the Patient Health Questionnaire (PHQ), available in the electronic record, will be offered to patients in clinic (paper-based surveys or completed online with the assistance of the LVN, MA, RN or other member of the clinical team administering the screening). Patients are free to refuse distress screening.

Control condition patients will receive the current standard of care (ad hoc distress screening at the clinician's discretion) and basic education about the study. Control sites will not be prohibited from using the PHQ. We anticipate a total sample of 1,200 newly diagnosed patients, 600 in each arm.

Intervention sites will receive audit and feedback of performance data and implementation facilitation throughout the 12-month intervention period (implementation strategies).

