- 5.5 Surveys: We will invite all newly diagnosed breast cancer patients at the intervention and control sites to complete two short patient-reported outcome surveys, the Functional Assessment of Cancer Therapy for Breast Cancer (FACT-B) and the Breast Cancer Prevention Trial Symptom Checklist (BCPT). Those who agree to participate will be asked to complete these two brief surveys at 3 time points (3-, 6- and 12-months).

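### The power claimed in section 14.1 at effect 0.2 and ICC 0.007 is not reached with 3 versus 3 centers, and it falls further for the survey outcomes, for which no response allowance is made

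*Combined protocol and SAP*

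**What the plan says.** Section 14.1 sets its target with "To achieve 80% power with a significance level of 0.05" and gives one range of effects: "For all outcomes, we expect relatively small standardized effect sizes (measured in terms of z-scores) ranging from 0.2-0.4". The per-center requirement is said to run from 20 (effect 0.4, ICC 0) to about 400 (effect 0.2, ICC 0.01). The conclusion is "we should be adequately powered to detect effect sizes as small as 0.2, given ICCs no greater than 0.007", and its basis is an anticipated 50 to 300 cases at each site. The section calls this a lower bound, because some centers may have more patients. These are counts of diagnosed patients, entered into the cohort without exclusion.

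Section 3.0 fixes the design: "There will be 6 KPSC medical centers participating in total: 3 intervention sites and 3 control sites", and "We anticipate a total sample of 1,200 newly diagnosed patients, 600 in each arm", a mean of 200 per center.

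The patient-reported outcomes come from a smaller group. Section 4.8 says "All eligible patients who speak English or Spanish will be invited to participate in a survey of patient-reported outcomes". Sections 5.5 and 13.5 instead say that every newly diagnosed patient is invited. All three limit data collection to those who accept; section 5.5 reads "Those who agree to participate will be asked to complete these two brief surveys at 3 time points", meaning 3, 6 and 12 months. No language share, response rate, attrition rate or survey-specific power is given. Section 14.2 provides for missing waves in the choice of model, but not in the sample size.

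**The concern.** The heading above section 14.1 is Aim 1, which names patient-reported outcomes, and section 4.10 lists FACT-B and BCPT as secondary outcomes. A reader will therefore apply the single power conclusion to them. Yet the number of patients behind that conclusion is the diagnosed cohort, not the survey responders.

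FACT-B and BCPT are the only planned direct reports by patients of well-being and symptoms that are compared between arms. A null FACT-B result would be read against 80% power at 0.2 SD. If the trial does not have that power, an uninformative result could be taken as evidence of no effect. The check below asks whether the claim holds with complete data, and how much further it falls with partial response.

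**Working it through.** **Inputs.** From section 14.1: alpha 0.05 (sidedness not stated; two-sided used), power 80%, effect 0.2 SD, ICC 0.007. From section 3.0: k = 3 centers per arm and m = 1,200/6 = 200 patients per center. Assumed here: equal center sizes; survey response of 100%, 70%, 50% or 30%, because the documents give no rate.

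**Formulas.** With SD 1, SE = √[(2/k)(ICC + (1 − ICC)/m)]. Normal power = Φ(effect/SE − 1.96). The small-sample version uses a non-central t with 2k − 2 = 4 degrees of freedom. Detectable effect at 80% power (normal) = 2.802 × SE.

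**The plan's own figures first.** With 3 centers per arm they do not reproduce:

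| Case | Plan, per center | 3 vs 3, normal | 3 vs 3, t on 4 df |
|---|---|---|---|
| effect 0.4, ICC 0 | 20 | 33 | 59 |
| effect 0.2, ICC 0.01 | about 400 | not attainable | not attainable |
| effect 0.2, ICC 0.007 | within 50 to 300 | about 1,541 | not attainable |

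The second row follows from the between-center term alone. As m grows without limit, SE tends to √(2 × 0.01/3) = 0.0816, and 2.802 × 0.0816 = 0.229, which is above 0.2. At 200 per center, the largest ICC that gives 80% power (normal) is 0.0027; at 300 per center it is 0.0043. A one-sided test does not rescue the claim at 200 per center, since 367 would be needed at ICC 0.007 (normal).

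The stated figures do match a calculation with 6 centers per arm (t on 10 df, two-sided): 21 and 412 per center, and 81.4% power at ICC 0.007 with 200 per center. That this basis was used is an inference from the match; the document does not say so.

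**Complete data, 3 vs 3.** SE = √[(2/3)(0.007 + 0.993/200)] = √[(2/3)(0.011965)] = 0.0893. Then 0.2/0.0893 = 2.239 and Φ(2.239 − 1.96) = 61%. With t on 4 df, power is 40%. The detectable effect is 2.802 × 0.0893 = 0.25 SD. Larger centers do not close the gap: 300 per center gives 67.5%/45%, and 400 per center gives 71%/48% (normal/t). At 50 per center it is 32%/21%.

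**Survey outcomes, one wave, effect 0.2, ICC 0.007.**

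| Assumed response | m | SE | Power, normal | Power, t on 4 df | Detectable effect (normal) |
|---|---|---|---|---|---|
| 100% | 200 | 0.0893 | 61% | 40% | 0.25 |
| 70% | 140 | 0.0969 | 54% | 35% | 0.27 |
| 50% | 100 | 0.1062 | 47% | 30% | 0.30 |
| 30% | 60 | 0.1253 | 36% | 23% | 0.35 |

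**Using all three waves.** Averaging three complete waves with within-patient correlation ρ multiplies the within-center term by (1 + 2ρ)/3 and leaves the between-center term unchanged. For assumed ρ of 0.5 to 0.7 the factor is 0.667 to 0.80. At 50% response, SE is 0.0953 to 0.0998 and normal power is 56% to 52%. At full response it is 67.5% to 65%.

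**Does the survey gap depend on the number of centers?** No. On the 6-per-arm basis, 184 per center are needed at ICC 0.007, and 184/200 = 92%. Response below about 92% of a mean of 200 already gives less than 80% power: 75% at 70% response and 67% at 50%.

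**The case against.** The strongest reply is that non-response is not the main cause. This is right. A reader might infer that the claim holds for record-based outcomes and fails only for surveys, or that it would hold at 100% response. The first row of the survey table rules out both. Going from full to 50% response costs a further 14 points or so (normal) or 10 (t), while the shortfall with complete data is already 19 points (normal) or 40 (t).

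A second reply is that failure is shown at one corner, and this also stands. Section 14.1 gives effects from 0.2 to 0.4, and 0.007 is an upper limit for the ICC. At effect 0.4 and ICC 0.007, power is 99%/91% at full response, 96%/80% at 50% and 89%/67% at 30% (normal/t). At effect 0.2 and ICC 0, the normal approximation keeps 80% down to about 65% response, although t on 4 df gives only 74% at full response. So the documents do not support a reading that the trial is underpowered throughout, or that response alone defeats it. Still, 0.2 at 0.007 is the limit that the plan itself claims to meet.

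Third, the phrase covering all outcomes governs the effect sizes, not the sentence on adequate power. Grammatically that is so. But no other power statement is offered, and the aim above it includes the surveys.

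Fourth, these are secondary outcomes, and benefit to patients may also show in referral completion, emergency visits and hospitalizations. It would be too strong to call the surveys the only evidence of benefit. Finally, the language restriction is not settled, because sections 5.5 and 13.5 invite everyone. The restriction to those who agree is common to all three sections.

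**Conclusion.** The point holds, and section 14.1 is wrong as written. At effect 0.2 and ICC 0.007, with 3 versus 3 centers and 200 patients per center, power is about 61% (normal) or 40% (t) for any outcome with complete data, not 80%. For FACT-B and BCPT it is lower by an amount that depends on a response rate the plan does not state: 47%/30% at an assumed 50%, with a detectable effect of 0.30 SD against 0.25 SD at full response. Three averaged waves do not restore 80%.

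The result rests on equal center sizes, a two-sided test, the ICC at its stated limit and assumed response rates. The missing survey allowance is a defect in its own right, since it also matters on the more favourable 6-per-arm basis. The number of centers is the larger part of the shortfall.

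**What to change.** In section 14.1, replace the single conclusion with two statements, both recomputed for 3 versus 3 centers with small-sample degrees of freedom:

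- **Record-based outcomes:** power or detectable effect on all eligible patients, over a stated range of ICCs. This statement must be corrected; the present figures cannot be carried over.
- **Patient-reported outcomes:** the same on expected responders per center, stating the assumed language share, response rate and attrition across the three waves, and the within-patient correlation if the repeated measures are relied on.

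Give the number of centers per arm and the sidedness used, so that the figures can be reproduced. Reconcile section 4.8 with sections 5.5 and 13.5 on who is invited to the survey.

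The cost is a few lines of text. No patients are added and the design does not change, but the stated figures become less favourable.
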